Cannabis use will be measured with a parallel DDQ measure that will assess typical days used and typical number of hours high each day ($\alpha=.97$, Lee et al., 2013). The Marijuana Consequences Questionnaire and a modified version (Lee et al., 2021) will measure a broad range of negative cannabis consequences and evaluations of negative cannabis consequences ($\alpha=.89$). Motives for cannabis use will be assessed by a modified version of the Comprehensive Marijuana Motives Questionnaire (C-MMQ) (Lee et al., 2009). To assess risk for substance use disorder, we will use the Cannabis Use Disorders Identification Test-Revised (CUDIT-R; Adamson et al., 2010; $\alpha=.80$). Cannabis PBS will be assessed using an adapted version of the Protective Behavioral Strategies for Marijuana Scale (PBSM-36; Pedersen et al., 2017; $\alpha=.93$). Concerns related to alcohol or cannabis use will be assessed in the baseline survey using the Card Sorting Task from the Brief Drinker Profile (Miller & Marlatt, 1984). Simultaneous substance use will be assessed with the Other substance use will be assessed for lifetime and past month frequency using the Customary Drinking and Drug Use Record (CDDR; $\alpha=.70-.94$; Brown et al., 1998; Schafer & Brown, 1991) as well as an adapted version that assesses co-use of substances. Readiness to Change Questionnaire (Treatment Version Revised) will be adapted to assess readiness to change cannabis use (Heather & Hönekopp, 2008; SAMHSA, 2019). SAM use: Questions regarding SAM use will be adapted from the Monitoring the Future measure (Johnston et al., 2015): "Within the past 2 months, how often did you use alcohol at the same time as cannabis – that is, so that their effects overlap?" We will use similar items to assess simultaneous substance use with alcohol and other drugs. CAM use: CAM use is determined from the alcohol and cannabis measures (i.e., endorsement of both alcohol and cannabis use within the same timeframe; Lee et al., 2013). The Consideration of Future Consequences scale ($\alpha = 0.80$; Strathman et al., 1994) will assess the level to which participants weigh immediate and distant outcomes due to their consequences. Anxiety and depression will be measured using the PROMIS Anxiety v1.0 and PROMIS Pediatric Anxiety v1.1 Short Form ($\alpha=.96$; Cella et al., 2010). Participants will be asked to report their intentions for using both alcohol and cannabis over the next 2 months. Concerns relating to alcohol and cannabis use will be selected and ranked in the Card Sorting Task in the Baseline survey (Marlatt & Miller, 1984). Usability Items: At the 2-Month Follow-Up Survey, participants assigned to the intervention condition will receive items to assess the usability of the online and text message program. Please refer to Appendix B for measures.

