Participants in the intervention group will be given two opportunities to review a personalized monthly summary of alcohol use, cannabis use, and protective behavioral strategy use. The first personalized report will summarize weeks 1-4 of their daily surveys and will be delivered via email and text message on the day after the 12th daily survey window closes. The second personalized report will summarize weeks 5-8 of their daily surveys and will be delivered via email and text message on the day after the 24th daily survey window closes. The reports will include a past month summary page for both alcohol and cannabis that provides details on the past four weeks. The alcohol use summary page will display the number of drinks participants had and the number of alcohol PBS they used on Friday, Saturday, and the random day on which they received personalized PBS text messages. The cannabis use summary page will display the number of hours participants spent high and the number of cannabis PBS they used on Friday, Saturday, and the random day on which they received personalized PBS text messages. A separate summary page will display the number of days in the past month that participants reported using both alcohol and cannabis simultaneously with overlapping effects. The last page of the monthly summary report invites them to review alcohol and cannabis PBS and ways they can use these PBS most optimally. This page routes back to a module in the intervention titled “Tips and Strategies” which outlines a list of high-quality PBS examples for alcohol use (e.g. “Refuse to ride in a car with a driver who you know has been drinking”) and a list of high-quality PBS examples for cannabis use (e.g. “Consider alternate activities instead of using cannabis to cope with emotions such as sadness or depression, or decide to only use cannabis when not feeling sad or depressed.”) Participants are not required to interact with their monthly summaries and will not be compensated for doing so. However, the aim of the monthly summaries is to encourage participants to reflect on their total number of drinks and hours high per day, week, and month and their PBS use over the time that they have received daily surveys and personalized PBS text messages.

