Daily survey measures. Our strategy is to collect daily reports each morning after intervention participants received TM content (intervention group). Assessment-only control participants will receive daily surveys on the same schedule as intervention condition participants. **Yesterday's**

alcohol/cannabis use: Participants will report the number of standard drinks consumed the previous day, the number of hours they spent drinking, whether they used cannabis, number of sessions used cannabis, and how long they were high. SAM use will be assessed by asking “Yesterday, did you use alcohol and cannabis at the same time—that is, so that their effects overlapped?” (Patrick et al., 2019).

CAM use will be identified by the endorsement of alcohol and marijuana use the previous day, but responding “no” to the SAM use item. **Substance-related consequences** experienced the previous day will be assessed with items from alcohol and cannabis consequences scales. **Motives to use alcohol**

and cannabis will be assessed via modified versions of the Drinking Motives Questionnaire and the Marijuana Motives Questionnaire, respectively (Bonar et al., 2018). For **alcohol**, we will administer items used in our previous daily diary study of alcohol use ([name] et al., 2020). A modified Marijuana Consequences Questionnaire (Lee et al., 2021) will assess **cannabis consequences**, selecting acute items appropriate for daily-level measurement (Linden-Carmichael et al., 2020). We will assess

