behavioral risks not included above (e.g., other substance use). **PBS use and quality** the previous day will be assessed by having participants report which, if any, alcohol and/or cannabis PBS they used the previous day, and for those they report using, how well they implemented the PBS (i.e., quality) and how helpful they perceived the strategy to be. **Motivations to use PBS** will be assessed by asking why they selected to use those strategies that day, or why they did not select to use the strategies they reported not using. **Quality of PBS use** will be assessed by a series of items demonstrating examples of low, medium, and high quality use of each strategy, with participants being instructed to select which scenario best reflects how they utilized the strategy. **Readiness to change** (Miller & Rollnick, 2013; SAMHSA, 2019) will be assessed with “At this moment, on a scale of 0 to 10, how important is it for you to change your current drinking/cannabis use if you decided to?”. Finally, we will assess if participants are currently

under the influence of alcohol or cannabis when completing daily surveys.

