Daily Survey Filler Measures. For days when participants do not report drinking or cannabis use the previous day, they will be asked alternative questions to balance the length of the assessments and to reduce participant boredom with the surveys. Alternative questions will be programmed such that a new filler measure will be shown to a participant on each non-drinking and non-cannabis use day. We will assess participants motives and reasons for either limiting alcohol/cannabis use or not using alcohol/cannabis on a given occasion via the Motives for Abstaining from Alcohol Questionnaire ($\alpha = 0.88$; Stritzke & Butt, 2001), the Reasons for Limiting Marijuana Use Scale (Epler et al., 2010; Huang et al., 2011; Johnson & Cohen, 2004), the Reasons for Not Drinking Scale (O'Hara et al., 2014), and the Reasons for Alcohol and Cannabis Nonuse Scale (Stevens et al., 2021). The Fear of Missing Out scale (FoMO; $\alpha = .90$; Przybylski et al., 2013) will assess the level to which one perceives that others are having rewarding experiences while one is absent. The Consideration of Future Consequences scale ($\alpha = 0.80$; Strathman et al., 1994) will assess the level to which participants weigh immediate and distant outcomes due to their consequences. Self-compassion will be assessed using the Self-Compassion Scale ($\alpha = 0.88$; Raes et al., 2011). The Self-Monitoring Scale ($\alpha = 0.71$; Snyder & Gangestad, 1986) will assess the extent to which one is willing and able to influence how one's image is perceived. The Social Lives Scale ($\alpha = 0.76$; Deri et al., 2017) will assess participants' perception of other and their own social lives. The Locus of Control Scale ($\alpha = .70$; Rotter, 1971; Kourmousi et al., 2015) will assess participants' internal and external control of reinforcement. The Social Avoidance ($\alpha = .84$) and Social Fear scales ($\alpha = .85$; Heimberg et al., 1999; Liebowitz, 1987) will assess social phobia. Participants' level of satisfaction with life will be assessed by the Satisfaction with Life Scale ($\alpha = .87$; Diener et al., 1985). The Network of Relationships Inventory subscales (Emotional Support, Companionship, Companionship; $\alpha = .92-.93$; Furman & Buhrmester, 1985) will assess positive and negative features of participants' relationship with a best friend.

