H2d: We will examine whether days when young adults use alcohol alone, compared to both CAM and SAM use days, are associated with greater use of alcohol PBS, greater motivation to use alcohol PBS, less motivation for non-use of alcohol PBS, and higher quality of alcohol PBS use. Similarly, we will examine event-level associations between PBS use and consequences (alcohol and marijuana) to determine whether PBS are as effective at reducing consequences when CAM or SAM use occurs.

H2c and H2d utilize event-level data and can be tested with GLMM, which is also used for H2b. The 2-level model accounts for the clustering of observations whereby daily surveys (Level 1: day-level) are nested within individuals (Level 2: person-level). GLMM can accommodate unequal observations per person. We will employ an appropriate modeling distribution for all outcomes (e.g., zero-inflated Poisson distribution for count outcomes like consequences; normal distribution for PBS motivation). We will evaluate whether model assumptions are met (e.g., normality of error terms) so that data are modeled appropriately (Atkins & Gallop, 2007). Centering of predictors and controlling for the associated higher-level effects will be done based on standard practice and current recommendations. Biological sex and age will be person-level covariates in all analyses, and daily-level covariates will be alcohol use, cannabis use, weekend, and readiness to change in all analyses. We will also consider adding daily-level covariates related to the COVID-19 pandemic if deemed necessary. Due to the large number of models, p-values will be adjusted (Benjamini & Hochberg, 1995).

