Event-level designs using daily surveys produce rich and complex data sets that permit the examination of different types of associations among constructs, and these complex associations can be tested with GLMM. For instance, H2c specifies that on days when individuals' motivations to use PBS are elevated (i.e., higher than their own average level), they will report lower alcohol use. Here, PBS motivations is the predictor (person-centered) and number of drinks consumed that day is the outcome. A cross-level interaction between the predictor (Level 1) and condition (Level 2) can be tested to determine whether this effect is stronger among those in the intervention condition compared to the assessment-only control condition. GLMM specifications can easily be modified for the event-level data to test all the hypotheses specified by H2c and H2d. For instance in H2d, each day will be coded as: neither alcohol nor marijuana, alcohol alone, marijuana alone, CAM, or SAM. Then dummy codes will be created to make specific comparisons (e.g., alcohol alone days versus SAM use days).

3) *Data Storage and Confidentiality* – *Describe where the research data will be stored during the study and how it will be secured. The investigator must take necessary steps to maintain confidentiality of data. This*

includes coding data and choosing an appropriate and secure data storage mechanism which will prevent unauthorized access to data. State who will have access to the data. If data with subject identifiers will be released, specify the person (s) or agency to whom the information will be released and the purpose of the release. For specific language, please refer to the NTR IRB's [Data Storage and Security Guidance](#) document.

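### The event-level plan puts same-day alcohol and cannabis use into every H2c and H2d model as covariates, including models where they are the outcome, form part of it, or (if coded yes/no) duplicate the day types

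*Combined protocol and SAP*

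**What the plan says.** Section E.2 (Data Analysis and Data Monitoring) sets out one modelling approach for H2c and H2d. Sex and age enter at person level, and "daily-level covariates will be alcohol use, cannabis use, weekend, and readiness to change in all analyses". No model is exempted when one of these variables is its outcome. There is no lag, and the daily item that represents alcohol or cannabis use is not named.

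The same section defines the models to which the rule applies:

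- **H2c** relates daily motivation for, and quality of, protective behavioural strategies (PBS) to that day's alcohol use, CAM or SAM use, and negative consequences. In the worked example, "number of drinks consumed that day is the outcome".
- **H2d** sorts each day into five exclusive types (neither, alcohol alone, marijuana alone, CAM, SAM). It compares alcohol-alone days with CAM and SAM days on four alcohol-PBS outcomes: use, motivation to use, motivation for non-use, and quality.

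Section E.1 (Daily survey measures) gives the raw items. Alcohol is recorded as number of drinks and hours spent drinking. For cannabis the items are "whether they used cannabis, number of sessions used cannabis, and how long they were high". As to the co-use outcomes, "CAM use will be identified by the endorsement of alcohol and marijuana use the previous day", together with a no on the SAM item. SAM is same-day use of both with overlapping effects.

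**The concern.** A covariate that is the outcome, or one of the parts from which the outcome is built, takes over the variation that the hypothesis is about. In H2c this touches the alcohol-use and the CAM/SAM models. In H2d the day types are themselves functions of same-day alcohol and cannabis use, so a use covariate beside the day-type dummies can be redundant.

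The result could be a null or distorted motivation effect, an estimate that runs off to infinity, a coefficient that answers another question, or a contrast that depends on which column the software drops. If analysts repair these problems model by model after seeing the data, the choice of covariates is no longer prespecified.

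**Working it through.** The plan gives no figure to reproduce here; the check is of the model algebra.

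**Inputs.** From the daily items, alcohol can be coded as drinks, hours drinking or yes/no, and cannabis as yes/no, sessions or hours high: 3 × 3 = 9 codings. Assumption: every cannabis-use day has at least 1 session or more than 0 hours high.

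**(a) H2c alcohol use.** With identity link, the model drinks = b0 + b1·motivation + b2·drinks + other terms is fitted perfectly by b2 = 1 and all else 0, so b1 = 0 exactly. A simulated linear model (240 people × 24 days, assumed rates and effects) agrees: b1 is −0.335 without the drinks covariate, and 0 with it (R² = 1).

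Under a log link b1 is not forced to 0. Simulations, again with assumed inputs, illustrate this:

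- Poisson, alcohol days: rate ratio 0.83 without the drinks covariate, 1.00 with it.
- Poisson, all days: 0.846 without, 1.137 with (sign reversed).
- Over-dispersed Poisson, four runs: −0.196, −0.403, −0.179 and −0.400 without; 0.001, −0.043, 0.060 and 0.033 with.

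A yes/no alcohol covariate is constant on alcohol days and does no harm there. In the all-days Poisson simulation it gave a rate ratio of 0.830, the same as on alcohol days without any alcohol term.

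**(b) H2c CAM/SAM.** By definition, CAM-or-SAM = (any alcohol) × (any cannabis). With yes/no cannabis and any alcohol measure, take the linear predictor −K + (K − ε)·cannabis + b·alcohol, with b·(smallest positive alcohol value) > ε and b·(largest) < K. It is positive on every co-use day and negative on every other day, which is complete separation. The same holds with the roles exchanged. That gives 3 codings with yes/no cannabis plus 2 more with yes/no alcohol = 5 of 9. On alcohol days the pooled outcome is simply cannabis above zero, so all 9 separate.

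| Outcome | All days | Any-use days | Alcohol days |
|---|---|---|---|
| CAM-or-SAM pooled: complete separation | 5 of 9 | 5 of 9 | 9 of 9 |
| SAM alone or CAM alone: quasi-separation | 5 of 9 | 5 of 9 | 3 of 9 |

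Under complete separation the motivation or quality effect has no finite maximum-likelihood estimate. Under quasi-separation only the intercept and the separating use term diverge. With yes/no cannabis on alcohol days, the alcohol-alone days then contribute nothing to the likelihood, and what remains is SAM versus CAM among co-use days. A simulated SAM logistic model (assumed rates, no random effect) shows it: motivation was −0.395 (SE 0.060) at 10, 20 and 25 iterations, identical to the fit on cannabis days only. On all days it was −0.320 (SE 0.054), also stable.

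The alcohol-day column matters because quality is asked only for strategies used, and "For days when participants do not report drinking or cannabis use the previous day, they will be asked alternative questions". Alcohol-PBS predictors may therefore exist mainly on alcohol days. That is an inference; the plan does not say so.

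**(c) H2d.** With intercept, four day-type dummies and two use covariates there are 7 columns on all days; on alcohol days there are 5. If cannabis is yes/no, cannabis = marijuana-alone + CAM + SAM. Adding k to its coefficient and subtracting k from those three leaves every fitted value unchanged but shifts alcohol-alone minus CAM, and minus SAM, by k. Those contrasts are not estimable; CAM minus SAM is.

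| Coding | Rank, all days | Rank, alcohol days | Alone vs CAM, vs SAM |
|---|---|---|---|
| drinks + yes/no cannabis | 6 of 7 | 4 of 5 | not estimable |
| both yes/no | 5 of 7 | 3 of 5 | not estimable |
| drinks + sessions or hours high | 7 of 7 | 5 of 5 | estimable |

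Adding weekend and readiness leaves the deficits unchanged. Person-mean centring with the person means kept, as the plan intends, does not help (rank 9 of 10, or 12 of 14 with all terms centred). The PBS-by-day-type interactions remain estimable. With a cannabis amount, the contrast refers to CAM or SAM days at zero amount, which is an extrapolation.

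**The case against.** The strongest reply is that nobody would adjust a variable for itself. The worked H2c example does not repeat alcohol use among its terms, and Section E.2 says that specifications can be modified. For the drinks model, a slip in writing is the natural explanation. But the sentence is unconditional and no rule for leaving a covariate out is given. The need to leave cannabis out of the CAM/SAM models is also less obvious than the need to leave drinks out of the drinks model.

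A second reply is that cannabis is quantified elsewhere by time high: "typical days used and typical number of hours high each day" in the baseline and follow-up measures, and "number of hours participants spent high" in the monthly summaries. With that coding H2d has full rank when alcohol is entered as drinks. This stands, and it is why the H2d part is conditional. It does not select the daily covariate, and it does not rescue a pooled CAM-or-SAM outcome on alcohol days.

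Several stronger conclusions are tempting, and the documents do not support them:

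- *The drinks model cannot show the effect.* True only under an identity link. The plan describes a log link for counts such as alcohol use under H2b, and count distributions for H2c/H2d. In one of the four over-dispersed runs the hypothesised sign survived.
- *All CAM/SAM models fail to converge.* Only the pooled outcome loses a finite estimate of the tested effect. The plan does not say whether CAM and SAM are pooled.
- *Six H2c models (three outcomes × two predictors) are damaged whatever the coding.* A yes/no alcohol term leaves two of them, the alcohol-use models, unharmed on alcohol days.
- *Every cannabis term must leave H2d.* Adjusting for an amount is estimable and is a choice of estimand.

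**Conclusion.** The covariate rule is wrong as written and should be corrected before the daily data are analysed.

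- **H2c alcohol use:** a same-day alcohol quantity is the outcome or closely tied to it. With drinks on both sides the tested coefficient is 0 (identity link) or distorted, usually strongly attenuated (log link).
- **H2c CAM/SAM:** the covariates are components of the outcome. If pooled, there is no finite estimate in 5 of 9 codings on all days and 9 of 9 on alcohol days. If separate, the estimate is finite, but with yes/no cannabis it is conditional on cannabis use, which is not the H2c question.
- **H2d:** 4 outcomes × 2 contrasts = 8 contrasts are lost, only under yes/no cannabis (3 of 9 codings). CAM versus SAM and the PBS-by-day-type interactions are unaffected.

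The rank and separation results follow from the definitions, given that every day type occurs and that cannabis amounts are above zero on use days. If some use days report 0 hours high, separation of the pooled outcome on alcohol days under that coding becomes quasi. The simulated coefficients are illustrations only. The damage is confined to secondary event-level hypotheses, since feasibility and acceptability are primary for Aim 2.

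**What to change.** Replace the sentence that applies one daily covariate set to every model with a list per outcome:

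- **H2c alcohol use:** no same-day alcohol term.
- **H2c CAM/SAM:** no same-day alcohol or cannabis terms; state whether CAM and SAM are pooled or separate.
- **H2d day-type contrasts:** no yes/no cannabis or yes/no alcohol term beside the day-type dummies. If a cannabis amount is kept, name the item and state that the contrast is conditional on that amount.
- **Consequence models:** keep same-day use as planned.
- **All models:** keep weekend, readiness to change, sex and age, and name the daily item behind every use covariate retained.

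The cost is a change of wording in the analysis section. It needs no new data and no extra models.
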